5.7 REPORTING OF SERIOUS ADVERSE EVENTS

Any SAE occurring after the subject signs the informed consent form must be reported to the Sponsor by phone, or e-mail within 24 hours of the time the investigator becomes aware of the SAE (Table 3). Urgent reporting of SAEs is required for the following reasons:

1. To enable the Sponsor to fulfill the reporting requirements to the appropriate regulatory authority
2. To facilitate discussion between the Sponsor and the investigator about appropriate follow-up measures (if necessary)
3. To facilitate the Sponsor's rapid dissemination of information about AEs to other investigators or sites in a multicenter study
4. To facilitate reporting unanticipated problems involving risk to subjects to the IRB

Table 3. Timeline for Reporting SAEs

Initial SAE Report		Follow-up SAE Report	
Time Frame	Documents	Time Frame	Documents
24 hours	SAE report	7 days	Updated SAE report

SAE: serious adverse event.

The SAE report will be completed as thoroughly as possible, including the following:

- Subject identification information
- Event term
- All available details about the SAE
- Causality of each SAE
- Signature of the investigator

The SAE report will be forwarded to the Sponsor within the designated time frames. If additional information to complete the SAE report form is needed, the investigator

will not wait before notifying the safety department of the SAE. The SAE report form will be updated by the investigator when additional information is received.

5.8 FOLLOW-UP OF ADVERSE EVENTS AND SERIOUS ADVERSE EVENTS

After the initial AE or SAE report, the investigator is required to follow each subject until the occurrence of one of the following:

- The condition resolves.
- The condition stabilizes.
- The event is otherwise explained.
- The subject is lost to follow-up.
- 30-days after the end of study (EOS visit).

The appropriate SAE report form will be updated once the SAE resolves, stabilizes, or is otherwise explained or until the subject is lost to follow-up. The investigator will also ensure that updates include any supplemental data that may explain causality of the SAE(s).

New or updated information will be recorded on a copy of the initial SAE report form, with all the changes signed and dated by the investigator or designee. The updated SAE report form will then be signed and dated by the investigator and resubmitted to the pharmacovigilance department.

5.9 PREGNANCY

When study personnel become aware of a subject's (or subject's partner's) pregnancy, the site personnel must report the pregnancy to the Sponsor's medical monitor within 24 hours by using the pregnancy notification form. The female subject will discontinue Study drug. The pregnancy will be followed until there is an outcome, and the outcome is reported to the Sponsor.

6.0 STUDY OR SITE TERMINATION AND SUBJECT DISCONTINUATION

6.1 SUBJECT DISCONTINUATION

Subjects will be encouraged to complete the study; however, they may voluntarily withdraw at any time. The investigator will provide a written explanation of the reason for discontinuation in a source document and this information will be recorded on the appropriate CRF page. If a subject withdraws before completion, every effort should be made to complete the Day 84 assessments scheduled during the End of Study visit.

A subject may be removed from the study for the reasons described in [Section 6.1.1](#) through [Section 6.1.5](#).

6.1.1 Adverse Event

If a subject experiences an AE that, in the judgment of the investigator, the sponsor, or the medical monitor, presents an unacceptable consequence or risk to the subject, the subject may be discontinued from the study.

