2.4 REPLACEMENT OF DROPOUTS

Subjects participating in the exposure group that do not complete all required blood draws will be replaced. Subjects that do not complete the blood draws but wish to continue in the exposure group may be continued and will be evaluated for efficacy and safety after 4 treatments.

Those patients that do not complete the full treatment due to protocol adherence or request to be discontinued from the study will be not be replaced. Subjects who do not complete the safety and efficacy evaluation period will be considered dropouts. Dropouts will not be replaced. In the event a patient requests to be removed from the study due to study related adverse experiences or additional spreading of disease, data will be collected and analyzed as a treatment failure and not replaced.

If a subject becomes able to provide informed consent or a legally authorized representative is located after randomization, information about the trial should be provided and procedures from the IRB/ethics committee will be followed. The subject or legally authorized representative can withdraw consent after being notified without any penalty or changes to care. Data collected to the point that consent is withdrawn are still assessable by the principal investigator. If subjects do not want their data that has already been submitted or specimens utilized they will need to submit a request in writing to the Investigator for removal of their information.

3.0 DRUGS AND DOSAGES**3.1 IDENTIFICATION AND DESCRIPTION OF INVESTIGATIONAL PRODUCT****3.1.1 Investigational Product**

VP-102 is a cantharidin solution [0.7% (w/v)] in a film-forming excipient formulation. Once applied to the skin, solvents in the Study drug evaporate leaving behind a thin, flexible and resilient film. The Study drug is light purple in color and has been manufactured under good manufacturing practices (GMP).

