6.1.4 Refusal of Investigational Product Administration

Any subject refusing clinical trial material for any reason will be discontinued from the study, and the reason(s) will be documented on the appropriate CRF page. Reasonable efforts should be made to monitor the subject for AEs and to complete follow-up assessments after treatment discontinuation. These efforts should be documented on the appropriate CRF page.

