9.4. Handling of Dropouts or Missing Data

All subjects who receive treatment will be evaluated in the ITT population. Subjects who do not complete all of the scheduled blood draws will be replaced. In the event a subject requests to be removed from the study due to study related adverse events or additional spreading of disease, data will be collected and analyzed as a treatment failure and not replaced.

Unless described otherwise in subsequent sections, analyses will be carried out with the data available using no imputation for missing data. A description of how missing data will be handled for the primary endpoint and secondary endpoints is included below.

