9.4.1. Handling of Missing Data for Complete Clearance Endpoint

The efficacy endpoint, proportion of subjects exhibiting complete clearance of all treatable lesions, is to be assessed a maximum of four times during the study. Assessments are to be done at Day 21, Day 42, Day 63 and Day 84 (EOS).

Subjects who do not have an assessment of complete clearance of all treatable lesions at any of the scheduled assessments will be considered to have missing data for this endpoint. Since the endpoint is complete clearance on or before Week 12, a subject will be considered to have met the condition of complete clearance if that subject has at least one assessment of complete clearance, regardless of what other assessments of clearance may be missing. If a subject has only non-missing assessments of not achieving clearance, then that subject will not be considered to have cleared. If a subject is missing all assessments of clearance, then that subject will be considered to have not cleared.

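### The treatment-failure rule covers only subjects who ask to leave, so a child removed for a drug reaction by the study side can be carried forward as a ≥90% responder

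*Protocol*

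**What the plan says.** Both documents contain one treatment-failure rule, triggered by a request from the subject. Protocol 2.4 opens it with "In the event a patient requests to be removed from the study due to study related adverse experiences or additional spreading of disease". SAP 9.4 has the same trigger: "In the event a subject requests to be removed from the study due to study related adverse events or additional spreading of disease".

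The protocol also provides exits that the subject need not request. Under 6.1.1 a subject may be discontinued when an adverse event, "in the judgment of the investigator, the sponsor, or the medical monitor, presents an unacceptable consequence or risk to the subject". Under 6.1.4, "Any subject refusing clinical trial material for any reason will be discontinued from the study". Neither section says how the subject is scored for efficacy. Protocol 2.4 has a general label, "Subjects who do not complete the safety and efficacy evaluation period will be considered dropouts", but it does not make dropouts failures.

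Subjects outside the failure rule go to the defaults:

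- SAP 9.4: unless a later section says otherwise, "analyses will be carried out with the data available using no imputation for missing data".
- SAP 9.4.1 (complete clearance): "a subject will be considered to have met the condition of complete clearance if that subject has at least one assessment of complete clearance". A subject with only non-zero counts, or with no count, is not cleared.
- SAP 9.4.2 (≥90% reduction, percent change, change): a missing EOS count is filled by LOCF. If only the baseline count exists, the value stays missing.
- SAP 5: missing values are left out of percentages unless stated otherwise.

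**The concern.** A treatment-failure rule exists so that a child who stops because of the drug, or because the disease is spreading, does not help the response rate. For that purpose it should not matter who made the decision. Here it does. The rule catches the family that asks to stop, but not the child whom the investigator, sponsor or medical monitor takes out for the same reaction.

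The plan expects such exits: SAP 11.2 schedules a table of treatment-emergent events leading to study discontinuation. A child could appear in that table and also be counted as a ≥90% responder. In a study of at most 40 subjects, each such child is visible in the proportion.

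**Working it through.** The documents give no removal rate, response rate or power figure on this point, so there is no stated figure to reproduce. The check follows each type of exit through the rules and then sizes the effect.

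**1. Which rule applies to an exit for a study-related adverse event**

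| Exit | Source | Failure rule triggered? | Default if not |
|---|---|---|---|
| Subject or parent asks to leave | Protocol 2.4, SAP 9.4 | Yes | – |
| Investigator, sponsor or medical monitor removes | Protocol 6.1.1 | No | SAP 9.4.1, 9.4.2 |
| Subject refuses further drug | Protocol 6.1.4 | Unclear; can be read as a request | SAP 9.4.1, 9.4.2 |

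**2. ≥90% reduction with a post-baseline count but no EOS count.** SAP 10.3 gives percent change = (post-baseline − baseline) / baseline × 100. Take an illustrative child with 30 lesions at baseline and 3 at the last visit before removal. LOCF carries the 3 forward: (3 − 30) / 30 × 100 = −90%, which SAP 10.2 classes as ≥90% reduction. A non-zero last count qualifies only if it is at most one tenth of baseline, so the baseline must be at least 10 (1/10 = 10% remaining).

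**3. ≥90% reduction with only a baseline count.** A child removed after the first application with no later count stays missing (SAP 9.4.2) and drops out of the percentage (SAP 5). Assuming 8 responders among 16 subjects and one such child among the other 8:

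- child excluded: 8/15 = 53.3%
- child counted as a failure: 8/16 = 50.0%

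For complete clearance, SAP 9.4.1 scores the same child as not cleared, so the two endpoints treat one exit differently.

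**4. Complete clearance.** A child with a zero count before any removal finishes the study that day (Protocol 2.1 and schedule footnote c), so is not later removed. A removed child with non-zero counts only, or none, is already not cleared. That leaves a zero count recorded at or after removal, at a visit before Day 100 (SAP 10.1), for instance at the assessments that Protocol 6.1 seeks from early leavers.

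**5. Size.** If k removed children are scored as responders instead of failures, the proportion shifts by k/n. The sizes are n = 40 (16 + 16 + 8, maximum enrolment), n = 32 (16 + 16, no replacements) and n = 16 (the target for Exposure completers; SAP 9 also analyses efficacy in that population). The values of k are assumptions.

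| n | k = 1 | k = 2 | k = 3 |
|---|---|---|---|
| 40 | 2.5 points | 5.0 | 7.5 |
| 32 | 3.1 | 6.25 | 9.4 |
| 16 | 6.25 | 12.5 | 18.75 |

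Illustration with n = 16, k = 2 and an assumed 12 responders: 12/16 = 75.0% (exact 95% CI 47.6 to 92.7) becomes 10/16 = 62.5% (35.4 to 84.8).

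**The case against.** A reader might infer that the gap inflates the complete clearance rate, the only efficacy endpoint that the protocol labels secondary. The documents do not support that, as step 4 shows. Where a zero count is recorded at or after removal but within the window, it is an observed clearance and meets the endpoint's own definition.

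Other points on the same side:

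- *LOCF applies only without an EOS count.* Protocol 2.3.1 and 6.1 ask sites to obtain EOS assessments from early leavers. This stands as a condition on the example. It reduces how often the problem arises but does not remove it.
- *Refusal is a family decision.* Refusing more drug because of a reaction can fairly be read as asking to stop. This stands: 6.1.4 is an ambiguity to settle, and the firm gap is 6.1.1.
- *The direction is not one-way for every endpoint.* LOCF from an early visit can understate response, because the child loses later treatments. A removed child below 90% at the last count is a non-responder under either rule. Only children already at ≥90% but not clear are rescored, along with the baseline-only children restored to the denominator. For the ≥90% proportion, both changes lower the reported figure or leave it the same.
- *Low stakes.* Efficacy is descriptive, with no formal comparisons (SAP 9.3, 9.6). Reasons for discontinuation are summarised (SAP 7.1) and subject data are listed, so a careful reader could find such a case. This stands and limits the weight of the point.

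**Conclusion.** The gap is real and limited. Both documents tie treatment failure to who asked for the exit, and removal under Protocol 6.1.1 falls outside that wording. The consequence lies mainly in the exploratory ≥90% reduction endpoint: 2.5 points per affected responder in 40 subjects, 6.25 in 16. There is also a smaller effect when a baseline-only child leaves the denominator. This assumes that at least one child is removed by the study side for a study-related event and either reaches ≥90% without clearing and has no EOS count, or has no post-baseline count. The documents do not say how many such children to expect; there may be none.

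A reader might also infer that identical data are certain to be scored failure on a parent's request and response on an investigator's decision. The text does not establish that. The SAP never says what value a treatment failure takes on any endpoint, and 9.4.2 contains no override, so LOCF could be applied to the parent-request child as well. The contrast holds only if failure is read as non-response, its natural meaning. Stating that value without widening the trigger would still leave study-side removals outside the rule. The change is worth making before the data are analysed, but the study's primary conclusion does not depend on it.

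**What to change.** 1. In SAP 9.4, and to match in Protocol 2.4, define the failure rule by the recorded primary reason for discontinuation (study-related adverse event or additional spread), whoever initiates it. Say that refusal of study drug under 6.1.4 for that reason is included.
2. In SAP 9.4.2 and 10.2, state that these subjects count as not ≥90% reduced, stay in the denominator, and that this overrides LOCF.
3. For complete clearance, keep the observed-count rule of SAP 9.4.1, or add a sensitivity analysis that counts these subjects as not cleared.

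No new data are needed: Protocol 6.1 requires the reason to be recorded and SAP 7.1 already summarises it. The cost is a few sentences in three SAP sections and one in the protocol, and a slightly lower reported ≥90% response if any such subject exists. The change affects scoring only, not when or why a subject is removed.

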6.1.2 Intercurrent Illness

A subject may be discontinued from the study if, in the judgment of the investigator, the subject develops an intercurrent illness or complication that is not consistent with the protocol requirements or that, in any way, justifies withdrawal from the study.

6.1.3 Noncompliance

After the investigator, the medical monitor, or study monitor consult (and the sponsor if appropriate), a subject may be discontinued from the study for the following administrative reasons:

- Failure to receive study medication or treatment as mandated by the specific instructions provided in [Section 3.0](#)
- Failure to comply with protocol requirements

6.1.4 Refusal of Investigational Product Administration

Any subject refusing clinical trial material for any reason will be discontinued from the study, and the reason(s) will be documented on the appropriate CRF page. Reasonable efforts should be made to monitor the subject for AEs and to complete follow-up assessments after treatment discontinuation. These efforts should be documented on the appropriate CRF page.

6.1.5 Withdrawal of Consent

Any subject who withdraws consent for any reason at any time during the study will be discontinued from the study, and the reason(s) will be documented on the appropriate CRF page. If subjects do not want their data that has already been submitted or specimens utilized they will need to submit a request in writing to the Investigator for removal of their information.

6.2 PREMATURE STUDY OR SITE TERMINATION

If the Sponsor, investigator, medical monitor, study monitor, or appropriate regulatory officials discover conditions arising during the study that indicate that the study should be halted or that the site should be terminated, this action may be taken after appropriate consultation among the Sponsor, investigator, medical monitor, and study monitor. Conditions that may warrant termination of the study include, but are not limited to, the following:

- The discovery of an unexpected, serious, or unacceptable risk to the subjects enrolled in the study
- A decision on the part of the Sponsor to suspend or discontinue testing, evaluation, or development of the product

A study conducted at a single site in a multicenter study may also warrant termination under the following conditions:

- Failure of the investigator to enroll subjects into the study at an acceptable rate

- Failure of the investigator to comply with pertinent regulations of appropriate regulatory authorities
- Submission of knowingly false information from the site to the sponsor, study monitor, or appropriate regulatory authority
- Insufficient adherence to protocol requirements

Study termination and follow-up will comply with the conditions set forth in International Council for Harmonisation E6, Guideline for Good Clinical Practice.

7.0 DATA COLLECTION AND PROCESSING AND STATISTICAL ANALYSIS**7.1 DATA COLLECTION AND PROCESSING**

Hard copy/paper CRF's will be used to capture study assessments and data. The investigator is required to prepare and maintain adequate and accurate source documents designed to record all observations and other data pertinent to the study for each study subject. The study coordinator or other delegated study personnel will enter data from source documents into the CRFs. A combination of both is also acceptable. All CRFs will be reviewed and source-verified by the study monitor centrally and during periodic site visits, and the study monitor will ensure that all data in the CRF are correct and complete. All information recorded on the CRFs for this study must be consistent with the source documentation (i.e., medical records). Before or between visits, the medical monitor or study monitor may conduct a preliminary medical review of the CRFs. Once the CRFs are completed and source-verified, the investigator must sign all required pages in the CRF, verifying the accuracy of all data contained in the CRF.

Training will be provided for CRF completion at the study initiation visit. All study personnel completing the forms must have the necessary education, training, and experience or any combination of these. The investigator will be responsible for documenting employee education, training, and previous experience for those assigned to support the required study activities.

If electronic data systems are used for documentation and data capture, the investigator must ensure that the systems are validated and that data are backed up as described in [Section 7.4](#).

7.2 STATISTICAL ANALYSIS

Prior to the analysis of the final study data, a detailed Statistical Analysis Plan (SAP) will be written describing all analyses that will be performed. The SAP may contain any modifications to the analysis plan described below. All statistical analyses will be performed with the SAS statistical software package (Version 9.3, SAS Institute Inc., Cary, NC).

7.2.1 General Overview

Subject disposition, demographics, baseline characteristics and Study drug exposure will be summarized by treatment group. The data will be summarized in tables, as appropriate, showing the number of subjects with non-missing data (n), mean, standard deviation, median, minimum, and maximum for continuous data and showing counts and percentage for categorical data. All data collected will also be presented in listings by subject and visit.

7.2.2 Sample Size

The primary objective of the study is to determine the presence or absence of systemic cantharidin exposure from application of VP-102. Thus, power calculations were not performed. Data will be summarized using descriptive statistics (sample size, mean, median, standard deviation, minimum, maximum) for continuous variables and frequencies and percentages for discrete variables. Corresponding by-subject data listings will be tabulated. There will be up to 40 subjects enrolled with the goal of 16 completing all blood draws in the exposure group. A maximum of 16 will be enrolled in the standard treatment group. The additional 8 subjects may be used for replacement patients. Any subject in the exposure group who does not complete all blood draws may continue to receive treatment, but will be replaced. No more than 16 subjects will be considered as completed Exposure group participants. At least 3 patients in the exposure group will be from 2-5 years of age. The definition of an enrolled will be those subjects that have signed informed consent and have been treated with at least 1 treatment.

Analysis Populations

Exposure Population: The Exposure population will include all subjects who have valid blood samples measured to assess exposure. This population will be used for the exposure analysis.

Intent-to-Treat Population: The intent-to-treat population (ITT) will include all subjects who meet the screening eligibility criteria and are enrolled in the study. This population will be used for the efficacy analysis.

Safety Populations: The safety population will include subjects who meet the screening eligibility criteria for the study and receive at least one application of Study drug. This population will be used for the safety analysis.

7.2.3 Exposure Analysis

Blood samples that will be obtained from subjects participating in the exposure group only. Samples will be obtained prior to the first treatment and at 2, 6 and 24 hours post application of study medication. Exposure will be assessed by looking for the presence of cantharidin in the plasma with a validated analytical method with a limit of detection of 1 ng/ml.

